OFFICIAL TITLE: Twelve-Month Prospective Evaluation of Clinical and Radiographic Outcomes of Pulpotomy Materials in Primary Molars

NCT Number: not yet assigned

Document Date: June 28, 2025

1. Background

Pulpotomy is a widely accepted treatment modality for cariously exposed primary molars. While several medicaments have shown favorable outcomes, the comparative effectiveness of emerging and traditional materials within the same patient cohort remains understudied. This study aims to prospectively evaluate the clinical and radiographic outcomes of four pulpotomy medicaments—MTA, Biodentine, Ferric Sulfate, and Sodium Hypochlorite—using a split-mouth randomized controlled trial design over a 12-month period.

2. Study Objectives

Primary Objective: To compare the 12-month clinical and radiographic success rates of MTA, Biodentine, Ferric Sulfate, and Sodium Hypochlorite in pulpotomy treatment of primary molars.

Secondary Objective: To determine the feasibility and effectiveness of a split-mouth design for pulpotomy comparisons in pediatric patients.

3. Study Design

Design Type: Prospective, split-mouth, randomized controlled clinical trial.

Participants: Healthy children aged 4–7 requiring pulpotomy in four primary molars due to deep caries.

Sample Size: A priori power analysis determined that at least 19 patients were required to detect statistically significant differences.

Randomization: Performed at the tooth level within each patient using sealed opaque envelopes prepared by an independent researcher. Clinical and radiographic assessors were blinded to treatment groups.

Inclusion Criteria:

- Age between 4 and 7 years
- Four primary molars indicated for pulpotomy due to deep caries
- Clinical signs of reversible pulpitis only
- Restorable teeth with normal periapical radiographs

Exclusion Criteria:

- Systemic illness
- Teeth with signs of irreversible pulpitis or radiographic pathology
- Uncooperative behavior impeding treatment

5. Interventions and Procedures

Local Anesthesia: 2% Lidocaine with 1:100,000 epinephrine

Isolation: Rubber dam

Access: High-speed handpiece with sterile water-cooled diamond bur

Coronal Pulp Removal: Low-speed round bur

Hemostasis: Achieved with sterile water-moistened cotton pellet

Groups and Materials:

Group I: 15.5% Ferric Sulfate – 15 s application

Group II: 5.25% Sodium Hypochlorite Gel – 1 min application

Group III: MTA – ~2 mm thick layer

Group IV: Biodentine – full chamber fill

Restoration:

Groups I-III: IRM base + stainless steel crown

Group IV: Biodentine fill + stainless steel crown

All crowns cemented with glass ionomer cement (Fuji I)

All procedures were performed by a single experienced pediatric dentist.

6. Follow-up and Outcome Measures

Follow-up Schedule:

Clinical: 3, 6, and 12 months

Radiographic: 6 and 12 months

Success Criteria:

Clinical: No pain, swelling, abscess, fistula, percussion sensitivity, or mobility

Radiographic: No furcation/periapical pathology, no internal resorption; Pulp canal obliteration was not deemed a failure

Evaluator Blinding:

- Clinical evaluation by two independent, blinded pediatric dentists
- Radiographic evaluation by a blinded pediatric dentist and radiologist

Disagreements were resolved through consensus. No pulp chamber masking was done, introducing a possible bias.

7. Statistical Analysis

All statistical analyses were performed using the Statistical Package for the Social Sciences (SPSS Version 26; IBM Corp., Armonk, NY, USA). Fishers exact test was used to compare clinical and radiographic outcomes at the 6- and 12-month follow-ups among the four groups. Success and failure rates were calculated based on a per-protocol analysis, which included 22 patients per group. Patients who did not complete the study protocol were excluded from the analysis. In addition, Cochrans Q test was applied to compare the clinical and radiographic success rates of the four pulpotomy materials (Biodentine, MTA, NaOCl, and Ferric Sulfate) at the 12-month follow-up. Treatment outcomes were dichotomized as success or failure. The test was calculated using data from all 22 patients in each group. The significance level was set at $p < 0.05$.

8. Ethical Considerations

Approval was obtained from Interventional Clinical Research Ethics Committee, (Approval No: 2021/77).

Written informed consent was obtained from the parents/legal guardians of all participants.

The study adhered to the Declaration of Helsinki and national regulations on human research ethics.

9. Data Handling and Confidentiality

All data will be anonymized and stored securely in password-protected databases accessible only to the research team. Personal identifiers will be removed during data analysis and reporting.

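### Tooth position is neither balanced in the described allocation nor used in either test; a tooth-adjusted comparison at 12 months would recover a little power at almost no cost

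*Combined protocol and SAP*

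**What the plan says.** Section 3 gives the design as "Prospective, split-mouth, randomized controlled clinical trial" and the allocation as "Performed at the tooth level within each patient using sealed opaque envelopes prepared by an independent researcher". How the envelope list was built is not stated: there is no rotation over positions and no stratification by arch, side or first versus second molar. Eligibility requires "Four primary molars indicated for pulpotomy due to deep caries", so any mix of molars qualifies.

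Section 7 names two tests. For the first, "Fishers exact test was used to compare clinical and radiographic outcomes at the 6- and 12-month follow-ups among the four groups"; this uses neither child nor tooth. For the second, "Cochrans Q test was applied to compare the clinical and radiographic success rates of the four pulpotomy materials" at 12 months; this blocks on child but has no term for tooth. Outcomes are binary ("Treatment outcomes were dichotomized as success or failure"), and on sample size, "The test was calculated using data from all 22 patients in each group". No adjusted analysis appears.

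**The concern.** A split-mouth design removes differences between children. It does not remove differences between teeth of the same child. Allocation is to a specific tooth, so tooth identity is known before randomisation, yet the plan makes no use of it in the allocation or in the analysis.

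If one class of tooth fails more often than another, a material that happens to receive more of that class looks worse through chance. With 22 teeth per material, one failure is 1/22 = 4.5 percentage points, so small shifts are visible in the success rates that form the primary comparison. At stake is some avoidable noise, and hence some power, in a small trial.

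**Working it through.** **Inputs from the documents.** 22 children analysed, four teeth and four materials each, so 22 teeth per material and 88 in all; binary outcome; significance level 0.05 (Section 7). Section 3 says "A priori power analysis determined that at least 19 patients were required to detect statistically significant differences", but gives no test, effect size, success rates or power. The figure of 19 therefore cannot be reproduced, and it cannot show whether tooth-to-tooth variation was allowed for.

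**Assumptions.** Two teeth of each class per child (for example two upper and two lower); orders drawn independently for each child; tooth-class effects and success rates as stated below. The documents supply none of these.

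**Step 1: size of the chance imbalance.**
- A given material falls on class A with probability 1/2 in each child. Its count has mean 22 × 1/2 = 11 and SD √(22 × 1/4) = 2.35.
- For two given materials, the per-child difference is −1, 0 or +1 with probability 1/3 each, so its variance is 2/3. Over 22 children the SD is √(22 × 2/3) = 3.83 teeth. A difference of 6 or more occurs in about 15% of lists.
- Across all four materials, simulation gives a mean gap between largest and smallest count of 5.5 teeth, and a gap of 6 or more in 47% of lists.

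**Step 2: what that does to a difference in success rates.** Shift = (gap/22) × tooth-class effect. For an assumed effect of 5 to 20 points:
- gap of 6 teeth: (6/22) × 5 = 1.4 to (6/22) × 20 = 5.5 points;
- one SD for a given pair: (3.83/22) × 5 = 0.9 to (3.83/22) × 20 = 3.5 points.

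The shift is random in sign.

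**Step 3: validity.** Under the null with free randomisation, Cochran's Q rejected in 4.1 to 4.8% of simulated trials, including when position mattered. Type I error is not inflated.

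**Step 4: power recovered by adjustment.** The adjusted test subtracts from each outcome the pooled failure rate of its tooth class, forms the between-material statistic, and takes p from permuting materials within child.

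| Assumed tooth-class difference | Gain over planned Cochran's Q | Gain over an unadjusted test of the same actual size |
|---|---|---|
| 0 points | about 1 point | 0 to 2 points |
| 5 to 10 points | 2 to 3 points | 0 to 2 points |
| 15 to 20 points | 3 to 4.5 points | 2 to 3 points |

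On an odds-ratio scale, with success near .95/.95/.80/.65, power went from Q to adjusted as follows: 83% to 83% (OR 1), 79% to 81% (OR 2), 79% to 83% (OR 4) and 75% to 82% (OR 9). Each cell had 1,500 trials and Monte Carlo error of about 1 point. In the same set-up with no material difference the adjusted test rejected in 4.5 to 5.5%, consistent with 5% given a standard error of √(0.05 × 0.95/1500) = 0.6 points.

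**Step 5: what balanced envelopes would do.** All 24 orders together put each material on class A 12 times. Leaving out two orders lowers each count by 0, 1 or 2, so with 22 distinct orders the gap cannot exceed 2. It is 0 only when the two omitted orders favour complementary pairs (4 of 23 choices), so the mean gap is 2 × 19/23 = 1.7 teeth. Unadjusted Q then becomes conservative: with Latin-square balance and about 70% success for every material, null rejection was 4.7%, 4.4%, 3.3% and 2.1% at position odds ratios of 1, 2, 4 and 9. Balance in the allocation should therefore be matched by adjustment in the analysis.

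**The case against.** The strongest case against acting has four parts.

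**The effect is assumed.** The documents give no difference in failure by tooth class. With none, imbalance costs nothing. This stands, and the loss can only be stated conditionally.

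**The gain is partly discreteness.** A reader might infer about 5 points of power from comparing the adjusted test with an unadjusted permutation test. Those two tests had different actual size: null rejection was 5.0% and 3.3%. Even with no tooth effect, adjustment seemed to raise power (43.2% to 45.5%, and 49.9% to 55.3%). Matched for size, that gain vanished (47.7% against 46.4%, and 56.4% against 56.2%). This stands; the smaller gains in the table are the ones to use.

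**Adjustment can cost power.** A linear F test with child, position and material lost about 1 to 2.5 points against its unadjusted form at odds ratios of 1 to 2. That belongs to the linear model. The permutation version showed no measurable loss, and it fits no model that few failures could make unstable.

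**It is too late, and one more analysis adds choice.** Sections 5 and 7 are in the past tense, so the envelopes are probably used. An analysis added now sits beside two existing tests and lies outside the standard tests named. Both points stand. They call for labelling it a sensitivity analysis and keeping Cochran's Q; they do not argue against reporting it.

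**Conclusion.** The point holds as an optional improvement. The plan describes no balance over tooth position, and neither named test uses position. If tooth classes differ in failure rate, noise is added that could be removed. Against Cochran's Q, the recoverable power is about 1 to 3 points for an assumed tooth-class effect of 0 to 10 points and about 3 to 4.5 points for 15 to 20 points, partly through reduced discreteness. Only an extreme assumption (odds ratio 9) took it to 6 or 7 points.

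Three stronger readings are not supported:
- **That the comparison is biased or the test invalid.** Allocation within child is random, Q keeps its size, and the 1.4 to 5.5 points is chance variation already covered by the test's error rate. It also refers to a gap of 6 teeth, which a given pair of materials reaches in only about 15% of lists.
- **That allocation was in fact unbalanced.** Section 3 is silent on how the list was made; the supportable statement is that no balancing is described.
- **That the loss is established and fully recoverable.** It depends on an effect the documents do not give, and the design remedy probably no longer applies.

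The imbalance figures also assume two teeth of each class per child, which the eligibility criteria do not require.

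**What to change.** **Section 7.** Keep Cochran's Q. Beside it, add a 12-month material comparison adjusted for tooth class (arch, or first versus second molar, with the choice stated): outcome minus the pooled failure rate of its tooth class, with p from permuting materials within child. Report a table of material by tooth class. Label the analysis post hoc if outcomes are already known.

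**Section 3.** State how the envelope list was built and whether it was balanced over position. If any allocation remains, number each child's four study teeth in a fixed order and fill the envelopes from a randomly ordered list of the 24 possible material orders. Use the adjusted analysis with it, because unadjusted Q is conservative under balance.

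**Cost.** One short extra analysis and one table, using tooth number; no extra children or visits. A 24-order list makes only the last one or two orders slightly more predictable.

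### Fisher's exact test, which assumes independent groups, is the only test at 6 months in this split-mouth trial; at 12 months it stands beside the matched Cochran's Q and neither is named decisive.

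*Combined protocol and SAP*

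**What the plan says.** Section 3 (Study Design) describes a split-mouth trial in children who each need four molars treated. Of the randomisation it says: "Performed at the tooth level within each patient using sealed opaque envelopes". With four materials, four molars per child and 22 patients in every group (Section 7), each analysed child is one matched set of four teeth.

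Section 2 sets the primary objective: "To compare the 12-month clinical and radiographic success rates of MTA, Biodentine, Ferric Sulfate, and Sodium Hypochlorite". Section 6 schedules clinical visits at 3, 6 and 12 months, and for films "Radiographic: 6 and 12 months".

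Section 7 (Statistical Analysis) names two tests:

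- For both 6 and 12 months: "Fishers exact test was used to compare clinical and radiographic outcomes at the 6- and 12-month follow-ups among the four groups".
- For 12 months only: "In addition, Cochrans Q test was applied to compare the clinical and radiographic success rates of the four pulpotomy materials". This uses all 22 patients and outcomes coded as success or failure.

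The significance level is 0.05. Neither test is called primary, confirmatory or supportive, and nothing is said about what happens if they disagree.

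**The concern.** Fisher's exact test compares independent groups. Here the groups are four teeth from the same mouths, and the design exists so that each child serves as its own control. Fisher uses only the four failure totals, so it cannot see which failures share a child. Cochran's Q can.

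Two gaps follow:

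1. **Six months.** The clinical and radiographic comparisons have no matched test at all, although the plan supplies one at 12 months.
2. **Twelve months.** The primary comparison has two tests of the same hypothesis at the same level and no stated precedence. If the order of the text means that Fisher leads, the unmatched test governs the primary objective.

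If outcomes within a child are positively correlated, Fisher is too conservative. A real difference between materials is then more likely to be reported as no difference. At 12 months the two p-values can fall on opposite sides of 0.05, with no rule for which one counts.

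**Working it through.** **Inputs from the documents.** 22 children with 4 teeth each = 88 teeth; one tooth per material per child; alpha 0.05; Fisher at 6 and 12 months; Cochran's Q at 12 months only. The plan gives no figure for either test that could be reproduced. It states no expected failure rates and no within-child correlation, so both are assumed below.

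**Step 1: two hypothetical data sets with the same totals.** Let f_j be the failures on material j, T their sum, and r_i the failures in child i. With four materials,

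Q = 3 × (4 Σ f_j² − T²) / Σ r_i(4 − r_i), referred to chi-square on 3 df.

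Take failures of 1, 1, 4 and 6 out of 22. Then T = 12, Σ f_j² = 1 + 1 + 16 + 36 = 54, and the numerator is 3 × (216 − 144) = 216. Fisher's p is 0.090 however the failures are spread over children.

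- *All in different children:* 12 children with r = 1 give a denominator of 12 × 3 = 36. Q = 6.0; chi-square p = 0.112, exact p = 0.130.
- *Concentrated in the same children:* one child with r = 4 (adds 0), three with r = 2 (3 × 4 = 12) and two with r = 1 (2 × 3 = 6) give a denominator of 18. Q = 12.0; chi-square p = 0.007, exact p = 12/3456 = 0.0035.

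In the first case both tests are non-significant. In the second they disagree, on totals that Fisher cannot tell apart.

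**Step 2: another clear disagreement.** Take failures of 0, 4, 4 and 5, where four children fail the same three materials and one further child fails one. T = 13 and Σ f_j² = 57, so the numerator is 3 × (228 − 169) = 177. The denominator is 4 × 3 + 1 × 3 = 15, so Q = 11.8. Under the null each of these five children has 4 equally likely patterns, 4⁵ = 1024 in all. Twelve of them are at least as extreme, so exact p = 12/1024 = 0.012. Fisher's p is 0.117.

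**Step 3: operating characteristics.** I simulated 22 children × 4 teeth with a normal latent variable shared within the child, 40,000 runs per cell. Fisher is the exact test on the 2 × 4 table. Exact Q is its permutation distribution given each child's number of failures. A latent correlation of 0.3, 0.5 or 0.7 corresponds to a tooth-level (binary) correlation of about 0.13, 0.25 or 0.41 at 10% failure.

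| Assumed failure rates | Quantity | 0 | 0.3 | 0.5 | 0.7 |
|---|---|---|---|---|---|
| 10% on every material | Size, Fisher | 2.9% | 1.6% | 0.8% | 0.3% |
| | Size, exact Q | 3.0% | 2.9% | 2.7% | 1.9% |
| | Size, chi-square Q | 3.9% | 3.7% | 3.4% | 2.6% |
| 5/5/25/25% | Power, Fisher | 57% | 55% | 53% | 50% |
| | Power, exact Q | 56% | 61% | 66% | 73% |
| | Power, chi-square Q | 57% | 64% | 69% | 76% |
| | Opposite verdicts, Fisher and chi-square Q | 5% | 10% | 17% | 26% |

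(Columns are latent correlation.) Part of the shortfall from 5% is sparse data, which Q shares. The part that grows with correlation is mainly Fisher's.

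At latent correlation 0.5, Q alone is significant in 16.42% of trials and Fisher alone in 0.29%. So 16.42 / (16.42 + 0.29) = 98% of the disagreements run one way. Fisher against exact Q disagrees slightly less often: about 14–15% at 0.5 and 23–24% at 0.7.

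**Step 4: the loss in children.** At latent correlation 0.5, exact Q with 22 children has 66.1% power; Fisher reaches 65.5% with 26 children and 68.9% with 27. At 0.7 the target is 72.8%; Fisher reaches 70.7% with 29 and 73.2% with 30. Fisher thus wastes about 4 to 5 children at 0.5 and about 8 at 0.7.

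**Step 5: sparser failures.** With 2/2/10/10%, power at latent correlation 0/0.3/0.5/0.7 is about 11/9/7/6% for Fisher and 11/12/13/14% for exact Q. Q is better whenever correlation is positive, but both miss most real differences.

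**The case against.** The strongest reply is that the primary objective already has its matched test. Cochran's Q is planned for exactly the 12-month outcomes, on all 22 children, so what is missing there is a label. Six months appears in no stated objective. The error is in the safe direction, and leaving two tests open does little to error control: declaring significance if either test rejects gave at most about 5.4% in the simulated nulls. The power gap also rests on assumed rates. If 6-month failures are few, Step 5 shows that changing the test would not rescue power.

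Much of this stands, and it limits the weight of the point. It does not remove it. The 6-month comparisons are planned and would be reported, and a non-significant result from a test that ignores the matching invites the reading that the materials do not differ. At 12 months a missing label matters whenever the two p-values straddle 0.05. If the plan's wording puts Fisher first, the omission favours the wrong test.

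**Conclusion.** The concern holds and should be fixed. As written, the 6-month analysis uses a test that does not fit matched teeth, and the primary 12-month comparison has two candidate answers with no precedence. The harm is lost power and an undetermined verdict, not inflated false positives.

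Its size depends on quantities the documents do not give. In the 5/5/25/25% scenario, exact Q gains 66 − 53 = 13 percentage points over Fisher at latent correlation 0.5 and 73 − 50 = 23 points at 0.7. At zero correlation there is no material difference. With very few failures neither test is adequate, so the remedy corrects the method without making the trial well powered. That Fisher does not suit matched teeth, and that no test is named decisive, follow from the text alone and need none of these assumptions.

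**What to change.** In Section 7:

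- Name Cochran's Q, with the child as block, as the decisive test for clinical and for radiographic success at 12 months.
- Apply the same test to both outcomes at 6 months.
- Drop Fisher's exact test, or label it descriptive.
- State which p-value of Q is used. The exact (permutation) version is preferable if failures are few; the chi-square version stayed below 5% in the null scenario above and is also defensible.
- Section 7 is written in the past tense. If results are already known, report the designation as post hoc.

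The cost is wording and a re-run on the same data, with no new patients or measurements. Choosing exact over chi-square Q gives up a little power: 66% against 69% at latent correlation 0.5 in the 5/5/25/25% scenario.

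### The only analysis set is 22 completing children, so a failure already recorded in an excluded child leaves the 12-month comparison; the direction of any bias is not shown

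*Combined protocol and SAP*

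**What the plan says.** Section 7 (Statistical Analysis) bases the rates on completers: "Success and failure rates were calculated based on a per-protocol analysis, which included 22 patients per group". It then gives the exclusion rule: "Patients who did not complete the study protocol were excluded from the analysis". For Cochran's Q at 12 months it adds: "The test was calculated using data from all 22 patients in each group". Fisher's exact test is named for 6 and 12 months.

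Section 6 schedules visits at which a failure can be recorded before month 12: "Clinical: 3, 6, and 12 months" and "Radiographic: 6 and 12 months". Section 2 sets the primary objective at 12 months: "To compare the 12-month clinical and radiographic success rates of MTA, Biodentine, Ferric Sulfate, and Sodium Hypochlorite in pulpotomy treatment of primary molars".

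Section 3 says of randomisation: "Performed at the tooth level within each patient using sealed opaque envelopes prepared by an independent researcher". On size it says: "A priori power analysis determined that at least 19 patients were required to detect statistically significant differences".

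The documents do not give the number enrolled, treated or excluded, the reasons for exclusion, a definition of completion, or a rule for scoring at month 12 a tooth that failed earlier. No second analysis set, missing-data rule or sensitivity analysis is described.

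**The concern.** The exclusion rule acts on children, not teeth. When a child is excluded, four teeth go, one from each material. If one of them met a failure criterion at 3 or 6 months, its outcome was known, yet it contributes nothing to the 12-month comparison. Because the set of 22 is the only one described, the same failure would apparently be missing at 6 months as well.

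Two results are at stake. One is the absolute success rate of each material, which depends on whether excluded children failed more or less often than completers. The other is the test between materials. In a set of 22, a p-value may rest on a handful of failures, and one child can then decide on which side of 0.05 it falls.

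**Working it through.** **The plan's own figures.** The minimum of 19 cannot be reproduced, because effect size, power, test and dropout allowance are not given. The 22 analysed could be 19 inflated for 10% dropout (19/0.90 = 21.1, rounded up to 22), but no such allowance is stated. The point does not depend on either number. All failure counts and dropout rates below are assumptions.

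**1. Effect of one child on Cochran's Q.** With k=4 materials, failures C_j per material, R_i per child and T in total, Q = 3(4ΣC_j² − T²)/(4T − ΣR_i²), on 3 df. If each failure is in a different child, ΣR_i² = T and Q = 4ΣC_j²/T − T. Children with no failure, or with failure on all four teeth, do not affect Q.

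| Completers' failures (22 children) | Q, p | One excluded child returned with an earlier failure | Q, p |
|---|---|---|---|
| 3/1/0/0 | 4·10/4 − 4 = 6.00, p=0.112 | 4/1/0/0 (same material as the 3) | 4·17/5 − 5 = 8.60, p=0.035 |
| 3/0/0/0 | 4·9/3 − 3 = 9.00, p=0.029 | 3/0/0/1 (another material) | 4·10/4 − 4 = 6.00, p=0.112 |

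The first row gains significance and the second loses it. These p-values use the chi-square reference. With an exact permutation reference these two pairs stay above 0.05, but others cross: 3/0/0/0 to 4/0/0/0 goes from 0.0625 to 0.0156, and 4/0/0/0 to 4/1/0/0 goes from 0.0156 to 0.0625.

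**2. Effect on a single rate.** A material at 22/22 falls to 22/23 = 95.7%, 22/24 = 91.7% or 22/25 = 88.0% if one, two or three excluded children had failed on it. A material at 19/22 = 86.4% rises to 20/23 = 87.0% or 22/25 = 88.0% if one or three excluded children had not.

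**3. Direction.** Assumed model: independent teeth, true success 95/95/85/75%, half of failures early, dropout d0 without and d1 with any early failure in the child. P(no early failure) = 0.975² × 0.925 × 0.875 = 0.7694. For the 75% material, P(no early failure in the other three teeth) = 0.975² × 0.925 = 0.8793. Completer success is 0.75[0.8793(1−d0) + 0.1207(1−d1)] / [0.7694(1−d0) + 0.2306(1−d1)]. With 10%/30% this is 0.6569/0.8539 = 76.9%.

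| d0/d1 | 95% material | 75% material | Gap (points) | Odds ratio |
|---|---|---|---|---|
| 10%/10% | 95.0 | 75.0 | 20.0 | 6.33 |
| 10%/30% | 95.4 | 76.9 | 18.5 | 6.28 |
| 5%/50% | 96.0 | 79.4 | 16.6 | 6.23 |
| 10%/0% | 94.8 | 74.1 | 20.7 | 6.37 |
| 20%/5% | 94.7 | 73.5 | 21.1 | 6.39 |

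Rates rise if children with an early failure complete less often, fall if they complete more often, and stay put if completion is unrelated. The near-constant odds ratio comes from assuming independent teeth; it is not a general property.

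**4. Chance of losing recorded failures.** Take four failing children, half with an early failure. The chance that a given one is excluded with a failure already on record is q = 0.5·d1, and P(at least 2 of 4) = 1 − (1−q)⁴ − 4q(1−q)³. This gives 1.4% (10%/10%, q=0.05), 11% (10%/30%, q=0.15), 26% (5%/50%, q=0.25) and 0% (10%/0%).

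**5. What bounds would look like.** Take 22 completers with two failures on one material, plus two excluded children. If each excluded child has a recorded failure on that material and six teeth are unknown, all 64 fillings give Q from 6 to 12, p from 0.112 to 0.007. If all eight teeth are unknown, the 256 fillings give Q from 0 to 12, p from 1.0 to 0.007.

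**The case against.** The strongest reply is that there may be nothing to correct. The documents give no exclusion count, and 22 exceeds the stated minimum of 19, so 22 may be everyone enrolled. A child with an early failure who attended every visit may also count as a completer. Both points stand, and either would leave no recorded failure lost. Neither can be checked from the documents, and the exclusion rule is stated without a count.

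A second reply is that the split-mouth design protects the comparison, since every material loses the same children. That is largely right for balance and is why the absolute rates are the more exposed quantity. Equal denominators do not, however, restore a failure that was removed.

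A third is that every count above is assumed. That is so. The calculations show sensitivity and do not estimate what happened.

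A reader might infer that exclusion inflated the success rates, or that it hid a real difference between materials. The documents support neither. Both depend on who was excluded and on which material they had failed, and none of that is given; the examples move both ways.

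It is also tempting to ask that any failure at any visit count as a 12-month failure for every child. For completers that would change the question from status at 12 months to cumulative failure. The clinical criteria include pain and percussion sensitivity, which might resolve. The exclusion problem does not require that change.

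**Conclusion.** The point holds as a defect in the stated rule. For any excluded child, a failure already recorded at 3 or 6 months is removed from the 12-month rates and both tests, and nothing in the plan brings it back. Whether this happened, how often and in which direction cannot be told from the documents.

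Under assumed counts, one child is enough to move Cochran's Q across 0.05 either way, and each excluded failure lowers a 22/22 rate by about 4 points. The model's shift in the 75% material runs from about −1.5 to +4.4 points, and the upper end needs half of the children with an early failure to drop out. These sizes rest on assumed failure counts and dropout rates, and the model shifts also on independent teeth. The matter should be fixed but is not fatal, and it disappears, apart from the scoring of earlier failures, if nobody was excluded.

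**What to change.** - Report the numbers randomised, treated, completed and excluded, with reasons, and define completion. If nobody was excluded, say so.
- Add an analysis of all randomised and treated children beside the 22-child per-protocol analysis. If the data have already been analysed, as the past tense of Section 7 suggests, disclose it as added after the fact.
- In that analysis, keep an excluded child's recorded failure as a 12-month failure on the outcome where it was recorded, with clinical and radiographic outcomes handled separately. Give best- and worst-case bounds for teeth of unknown status.
- State how a completer's earlier failure is scored at 12 months. If failure at any visit is used, label it cumulative failure by 12 months.

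The cost is some SAP wording and a small re-analysis of existing visit records. Success rates may fall slightly. The bounds may span p=0.05, as they do in the example with two excluded children, and they widen as more teeth are unknown.
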